9.3. Sample Size

Approximately four hundred (400) subjects will be randomly assigned via the minimization scheme to one of two preparations in a ratio of 1:1 (200 subjects per group) and undergo colonoscopy. Based on prior studies using a similar grading system, the success rate for PREPOPIK is expected to be no greater than 90%⁴. Assuming a similar success rate for BLI4700, a two-sided asymptotic 95% confidence interval for the difference in success rates between groups (BLI4700 – PREPOPIK) will result in a lower CI bound greater than -10%, with probability 90%. This result would establish the non-inferiority of BLI4700 to PREPOPIK for a non-inferiority margin of 10%.

Our sample-size calculations for equivalence tests with a binary outcome use the method of Chow et al⁵. If the PREPOPIK success rate is 90% and the BLI4700 success rate is also 90%, the sample size needed is n=310 (total across both study groups) for a non-inferiority margin of 10% and a target power of 90% with confidence 95%. Thus with n=400 subjects we will attain 80% power even with a dropout rate in excess of 20%.

In randomized studies, the purpose of the stratification is to eliminate the stratification factor from the error term, thereby potentially reducing variability⁶. Moreover, because the trial will use stratification in the design, for consistency we will employ a stratified test in the analysis. The CMH analysis on risk differences, by eliminating center effects, essentially renders the analysis equivalent to that of a single-center study. The sample-size calculation described above assumes a single stratum that is free of between-stratum variability and therefore effectively models the stratified analysis that we will conduct.

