9. DATA ANALYSIS

9.1. Study Endpoints - Efficacy

Primary efficacy will be assessed on the basis of a binary outcome of overall preparation success or failure. For statistical analyses, the following definition of preparation success and failure will be used:

Definition of successful preparation:

1. Overall Cleansing Assessment by the colonoscopist (Section 4.6.2) of “Excellent” or “Good” and does not satisfy any of the following failure criteria.

Definition of failed preparation:

1. Overall Cleansing Assessment of “Fair” or “Poor” by the colonoscopist
2. Any subject who did not have a colonoscopy based on the Investigator’s assessment of the cleansing (subject report of insufficient fecal output, unclear fecal discharge, etc.) or due to preparation related adverse events.
3. Any subject for whom cleaning was not adequate for evaluation

Unevaluable Subjects:

Subjects who were dispensed a kit but withdrew from the study prior to taking any preparation (including subjects who were disqualified subsequent to Visit 1 based on screening laboratory results) are excluded from the efficacy and safety analyses. Any subject who completely or partially took study preparation but did not have a colonoscopy due to non-preparation related reasons (e.g. lack of insurance, inability to return for colonoscopy) will not be included in the efficacy analyses. All treated subjects will be included in the safety analysis.

Success rate will be analyzed using CMH Chi-square adjusting for the effect of investigator site. The formal hypothesis test result (p-value) for treatment difference will be presented together with a two-sided 95% confidence interval for the difference.

Null Hypothesis $H_0: P_1 - P_2 \leq D_0$ versus Alternative Hypothesis $H_1: P_1 - P_2 > D_0$,

where P_1 is the success probability in the BLI4700 group, P_2 is the success probability in the PREPOPIK group (reference or control group), and D_0 is the acceptable margin of equivalence, which we set equal to -10% .

If necessary, we will pool the smallest centers into a “small-centers” stratum until each treatment arm in the smallest stratum has at least ten subjects.

If the test for non-inferiority is statistically significant, we will conduct a test of the superiority hypothesis:

Null Hypothesis $H_0: P_1 - P_2 \leq 0$ versus Alternative Hypothesis $H_1: P_1 - P_2 > 0$.

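### The interval that decides non-inferiority is called only asymptotic; ordinary non-score versions run slightly above 2.5% one-sided error, so a stratified score interval should be named

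*Combined protocol and SAP*

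**What the plan says.** Section 9.1 defines the primary analysis: "Success rate will be analyzed using CMH Chi-square adjusting for the effect of investigator site". The p-value "will be presented together with a two-sided 95% confidence interval for the difference". No method is given for that interval. The smallest centers are pooled "until each treatment arm in the smallest stratum has at least ten subjects".

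Section 9.3 contains the decision rule. It refers to "a two-sided asymptotic 95% confidence interval for the difference in success rates between groups" (BLI4700 minus PREPOPIK), which "will result in a lower CI bound greater than -10%, with probability 90" per cent, and says that such a result would establish non-inferiority. The section assumes 90% success in both arms, takes 90% as an upper limit for PREPOPIK, and plans 200 subjects per arm. It describes the analysis as a CMH analysis on the risk-difference scale and adds: "The CMH analysis on risk differences, by eliminating center effects, essentially renders the analysis equivalent to that of a single-center study".

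The documents do not name the variance formula, the stratum weights for the interval, or the number and size of sites.

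**The concern.** The main claim depends on one number, the lower 95% limit for P1 - P2. The plan's only description of how to compute it is the word asymptotic, and several standard intervals fit that word. Success is expected near 90%, where limits built on observed p(1-p)/n tend to be too narrow. Strata may be as small as ten per arm. At 90% success an arm of ten has no failures with probability 0.9^10 = 0.349, and such a cell adds nothing to a plug-in variance.

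If the limit is too narrow, an inferior preparation is declared non-inferior more often than the nominal 2.5%. If the method is left open, a borderline result can also depend on a choice made after the data are seen.

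**Working it through.** **Inputs.** From 9.3: margin -10%, two-sided 95% interval (one-sided 2.5%), 200 per arm, 90% success in both arms for power. From 9.1: stratification by site, with at least ten per arm in the smallest stratum after pooling. Assumed, because the documents do not give it: the site layout. The layouts run were one stratum of 200 per arm, 5 x 40, 10 x 20, 20 x 10, and a mix of 10 to 40 per arm.

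**Step 1. The plan's own figure.** SE = sqrt(0.9 x 0.1/200 + 0.9 x 0.1/200) = 0.030. Power = Phi(0.10/0.030 - 1.96) = Phi(1.373) = 91.5%. Exact enumeration for the Wald limit also gives 91.5%. The stated 90% is reproduced to within 2 points. (The separate figure of 310 in 9.3 is reproduced only at one-sided 5%; at one-sided 2.5% the same formula gives 380. That is a different matter, and 400 evaluable subjects cover it.)

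**Step 2. Error at the margin without strata.** Exact binomial enumeration of the probability that the lower limit exceeds -10% when P1 = P2 - 0.10, with 200 per arm:

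| Control rate | Wald | Score (Farrington-Manning) |
|---|---|---|
| 90% | 2.71% | 2.45% |
| 85% | 2.62% | 2.50% |
| 80% | 2.52% | 2.51% |

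**Step 3. Error at the margin with strata.** For stratum k, let x and y be the success counts on BLI4700 and PREPOPIK, n1 and n2 the arm sizes, and N = n1 + n2. The weight is w = n1 n2/N and the estimate is d = sum[w(x/n1 - y/n2)]/sum(w). Two variances were compared:

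- Plug-in: sum{w^2 [p1(1-p1)/n1 + p2(1-p2)/n2]}/(sum w)^2, with the observed stratum rates.
- Sato: [d sum(P) + sum(Q)]/(sum w)^2, where P = [n1^2 y - n2^2 x + n1 n2 (n2 - n1)/2]/N^2 and Q = [x(n2 - y) + y(n1 - x)]/(2N).

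Results at true rates of 80% versus 90% (400,000 simulated trials per layout, Monte Carlo standard error about 0.025 points):

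| Layout, per arm | Sato | Plug-in |
|---|---|---|
| 20 x 10 | 2.69% | 3.33% |
| 10 x 20 | 2.66% | 2.94% |
| 5 x 40 | 2.68% | 2.80% |
| mixed 10 to 40 | 2.70% | 2.97% |

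**Step 4. Why plug-in differs.** The expected value of observed p(1-p) is p(1-p)(n-1)/n. With n = 10 the variance is 10% too small, so the SE is too small by a factor of sqrt(0.9) = 0.95. Using n-1 denominators brings the 20 x 10 error down from 3.33% to 2.65%.

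**Step 5. The stratified score interval.** The stratified Miettinen-Nurminen limit was simulated with 40,000 trials per scenario (Monte Carlo standard error sqrt(0.025 x 0.975/40,000) = 0.08 points). Error was 2.2% to 2.6% over similar layouts and control rates of 85% to 95%. Power at 90% versus 90% was 89.7% to 90.3%.

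**Step 6. A borderline result.** Take 176/200 versus 184/200. The difference is -0.04 and the SE is sqrt(0.88 x 0.12/200 + 0.92 x 0.08/200) = 0.02993. The Wald limit is -0.04 - 1.96 x 0.02993 = -9.87%, so non-inferiority is declared. The Miettinen-Nurminen limit is -10.12%, so it is not.

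**The case against.** The strongest reply is that nothing in the plan is wrong. Score intervals are also asymptotic, so the recommended method already fits the wording of 9.3, and at the planned rate the excess for Wald or Sato is only about 0.2 points. That stands as to size. It does not close the gap, because the same wording equally permits limits that exceed 2.5%.

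Three stronger readings are tempting, and the documents do not support them.

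- **That the plan uses a Wald interval.** The word appears nowhere in the documents. It can only be inferred from asymptotic, a word that occurs in the sample-size section and not in 9.1.
- **That strata of ten per arm make the interval too narrow.** With Sato variance, a usual choice for a CMH risk difference, the error is the same for strata of 10, 20 or 40 per arm and matches the unstratified Wald figure. On that variance the single-center remark in 9.3 is fair. It concerns between-center variability, not variance estimation in small cells.
- **That the error is well above 3%.** The 3.3% needs plug-in variance and every stratum at exactly ten per arm, although ten is only a floor for the smallest stratum. The 3.6% seen at 85% versus 95% in that layout needs a control rate above the plan's 90% ceiling. Inverse-variance weights give 3.2% to 4.65% at 90% control success, and up to about 5.3% when site rates differ, but the plan describes a CMH analysis and does not mention such weights.

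**Conclusion.** The point holds in a limited form. The decisive limit has no stated estimator, weights or variance. At 90% control success and 200 per arm, the ordinary non-score CMH or Wald choices give one-sided error of about 2.7% (simple Wald, or Mantel-Haenszel with Sato variance) to 2.8%-3.3% (plug-in stratum variance). A score limit gives about 2.45%. The excess shrinks as control success falls: simple Wald is at 2.52% when the control rate is 80%.

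The unstratified figures are exact. The stratified figures rest on assumed site layouts, with 20 strata of ten per arm as the worst case. The inflation is mild and would matter only for a borderline result. This is a cheap improvement; it does not undermine the design.

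**What to change.** In 9.1, state that non-inferiority is concluded if the lower limit of the two-sided 95% stratified Miettinen-Nurminen (score) confidence interval for P1 - P2, with CMH weights over the pooled site strata, exceeds -10%. Use the same interval for the superiority step, with 0 in place of -10%. In 9.3, replace the general term asymptotic with a reference to that interval.

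The cost is one sentence, one matching edit and a standard software option. Power at 90% versus 90% with 200 per arm falls from about 91.5% to about 90%, a loss of roughly 1 to 1.5 points that still leaves the stated 90%.

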12.1. INFORMED CONSENT	37
12.2. INSTITUTIONAL REVIEW BOARD	37
12.3. AMENDMENTS TO THE PROTOCOL	37
12.4. DATA RECORDS.....	37
13. PUBLICATION AND AGREEMENT	38
14. INVESTIGATORS AGREEMENT	38
15. REFERENCES	39
16. APPENDICES	40

CLINICAL PROTOCOL SUMMARY SHEET

STUDY TITLE: A Safety and Efficacy Comparison of BLI4700 Bowel Preparation versus an FDA-approved Comparator in Adult Subjects prior to Colonoscopy

PROTOCOL: BLI4700-302

VERSION DATE: 7-28-17

IND NUMBER: 124,988

STUDY PHASE: 3

OBJECTIVE: To compare the safety and efficacy of BLI4700 bowel preparation to PREPOPIK as 2-day, split-dose bowel preparations prior to colonoscopy in adult patients.

STUDY DESIGN: This will be a randomized, parallel, multi-center, single-blind study.

SUBJECTS: Approximately 400 male and female adult subjects will be enrolled and undergo colonoscopy. It is anticipated that approximately 450 subjects will be randomized to achieve 400 completed colonoscopies.

STUDY MEDICATIONS: Treatment 1: BLI4700 bowel preparation
Treatment 2: PREPOPIK

DURATION: Subject participation in this study may last up to 60 days.

EFFICACY ENDPOINTS: Efficacy will be based on overall preparation success as determined by the blinded colonoscopist. Additional efficacy measures include the proportion of excellent preparations, segmental cleansing, time to cecum, volume of intraprocedural water used to improve visualization, percent of procedures that reach the cecum.

SAFETY ENDPOINTS: Safety endpoints include:

- Adverse event reports
- Changes in serum chemistry and hematology parameters
- Subject reported prep-related symptoms
- Orthostatic heart rate and blood pressure

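### Section 9.3 gives 310 subjects for 90% power, but its own two-sided 95% confidence interval rule needs 380; the planned 400 still suffices at 90% success in both groups

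*Combined protocol and SAP*

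**What the plan says.** Everything at issue stands in Section 9.3 of the combined protocol and SAP.

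- **Decision rule.** The first paragraph takes −10% as the limit and 200 subjects per group, and says that "a two-sided asymptotic 95% confidence interval for the difference in success rates between groups (BLI4700 – PREPOPIK) will result in a lower CI bound greater than" this limit; it puts the chance of that at 90%. It adds: "This result would establish the non-inferiority of BLI4700 to PREPOPIK for a non-inferiority margin of 10" per cent. Section 9.1 (Study Endpoints - Efficacy) likewise reports a two-sided 95% interval for the difference and sets the margin at −10%.
- **Required number.** The second paragraph takes 90% success in both groups and states that "the sample size needed is n=310 (total across both study groups) for a non-inferiority margin of 10% and a target power of 90" per cent. The confidence attached is 95%, with no statement of whether it is one-sided or two-sided.
- **Dropout.** The paragraph concludes that "with n=400 subjects we will attain 80% power even with a dropout rate in excess of 20" per cent.
- **Planning rate.** The first paragraph says "the success rate for PREPOPIK is expected to be no greater than 90" per cent; power is given at 90% only.
- **Enrolment.** The summary sheet says: "It is anticipated that approximately 450 subjects will be randomized to achieve 400 completed colonoscopies".

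**The concern.** A two-sided 95% interval whose lower limit must clear −10% is a one-sided test at alpha 0.025. A sample size that supports it has to use the same alpha. The 310 looked too small for that rule and about right for a one-sided 5% test, which corresponds to a two-sided 90% interval. No section of the document specifies such a test or interval.

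This paragraph is the justification of the sample size. A reader who accepts 310 as the requirement would conclude that 400 subjects can fall by 90 and still give 90% power. That matters for anyone judging a shortfall in completed colonoscopies, or the power of the per-protocol analysis (Section 9.4.3), which drops further subjects.

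**Working it through.** **Inputs, all from Section 9.3:** success 90% in both groups (true difference 0), margin 10 percentage points, 1:1 allocation, target power 90%, planned total 400 (200 per group).

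**Formula** (asymptotic, unpooled variance), n per group:

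n = (z_α + z_β)² × [p₁(1−p₁) + p₂(1−p₂)] / 0.10²

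The variance term is 0.09 + 0.09 = 0.18, so n = 18 × (z_α + z_β)².

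**Step 1: reproduce the plan's figure.** One-sided alpha 0.05, power 90%: 18 × (1.645 + 1.282)² = 154.1, rounded up to 155 per group, **310 in total**. This matches the plan exactly.

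**Step 2: apply the plan's decision rule.** One-sided alpha 0.025, power 90%: 18 × (1.960 + 1.282)² = 189.1, rounded up to 190 per group, **380 in total**. The difference is 380 − 310 = 70 subjects, and 70/310 = 23%.

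**Step 3: power under the two-sided 95% interval rule.** Power = Φ(0.10 / √(0.18/n) − 1.960), with n per group. The last column enumerates the binomial outcomes for the same (Wald) interval.

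| Total N | Loss from 400 | Power, normal approximation | Power, exact enumeration |
|---|---|---|---|
| 284 | 29% | 80.2% | 80.6% |
| 310 | 22.5% | 83.5% | 83.3% |
| 320 | 20% | 84.6% | 84.8% |
| 380 | 5% | 90.1% | 90.0% |
| 400 | 0% | 91.5% | 91.5% |

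For 310, as an example: √(0.18/155) = 0.03408; 0.10/0.03408 = 2.934; 2.934 − 1.960 = 0.974; Φ(0.974) = 0.835. With 1.645 in place of 1.960, the same 310 gives 90.1% (exact 90.2%).

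**Step 4: the two other claims in the section.** The 90% probability at 400 subjects holds (91.5%). The dropout claim also holds: 80% power needs 18 × (1.960 + 0.842)² = 141.3, so 142 per group or 284 in total, and 1 − 284/400 = 29%. For 90% power the tolerance is 1 − 380/400 = 5%, whereas the stated 310 implies 1 − 310/400 = 22.5%.

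**Step 5: could another method give 310 at 90% power?**

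| Method, 90% power | One-sided 0.05 | One-sided 0.025 |
|---|---|---|
| Unpooled, non-inferiority | 310 | 380 |
| Continuity-corrected | 348 | 418 |
| Farrington-Manning | 332 | 410 |
| Two one-sided equivalence tests (alpha for each) | 390 | 468 |

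Among these, 310 appears only in the first cell. Every entry at 0.025 is 380 or more.

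**The case against.** The strongest reply is that the origin of 310 cannot be established. At **80%** power the figure also arises in two other ways: from two one-sided equivalence tests at 0.05 each, and from Farrington-Manning at one-sided 0.025, which is the two-sided 95% rule. The section does speak of equivalence tests, and its next sentence moves to 80% power with dropout above 20%; a fall from 400 to 310 is 22.5%. The wrong entry might therefore be the 90%, not the 310. The cited textbook is not available here to settle it. This stands as far as the cause goes, and no cause is asserted here. It does not rescue the sentence, which ties 310 to "a target power of 90% with confidence 95" per cent.

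A second reply is that 95% confidence could be meant one-sidedly, so that 310 was computed correctly. Even so, it was computed for a different rule from "a two-sided asymptotic 95% confidence interval for the difference in success rates between groups" in the paragraph before it.

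A third reply is that little depends on the figure. The protocol itself draws only the weaker dropout conclusion, which is true, and 400 already counts completed colonoscopies, with about 450 randomized to reach it. That is right, and it limits the consequence to the written justification.

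Finally, 380 depends on the method. The section says asymptotic without naming a variance formula, and the planned test is a site-adjusted CMH analysis. This also stands: Farrington-Manning (410) or a continuity correction (418) would leave 400 slightly under 90% power. Both lie further from 310, so the mismatch grows.

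**Conclusion.** The statement is wrong as written. Under the section's own decision rule, 90% power needs 380 evaluable subjects, not 310, and 310 gives about 83.5%. The cushion in 400 at 90% power is 20 subjects, not 90.

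The planned trial size is adequate on the stated assumptions: 91.5% power at 400, and 80% power kept down to 284. These figures rest on 90% success in both groups, a 10-point margin, equal allocation and an unpooled asymptotic interval without site adjustment. Power falls if both groups share a rate below 90%. That is true of any such design and adds no weight here. For illustration, at assumed rates that the document does not give, 400 subjects yield 86.8% at 88% in both groups and 80.0% at 85%.

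**What to change.** Replace the n=310 sentence and the dropout sentence after it with text along these lines:

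> Assuming 90% success in both groups, a 10% margin and an unpooled asymptotic two-sided 95% confidence interval (one-sided alpha 0.025), 380 evaluable subjects (190 per group) provide 90% power. Power with 400 is 91.5%. From 400, 90% power is retained with losses up to 5%, and 80% power with losses up to 29%. If both groups have the same success rate and it is below 90%, power is lower.

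The present dropout sentence is true and could remain; the replacement makes it precise. If the sponsor's records show that 310 came from another method or from 80% power, the section should name that method and power, and still give the number for 90% power under the two-sided 95% rule.

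The cost is two sentences in one section. Enrolment, margin, test and decision rule do not change.

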9.4. Study Populations

The following populations have been defined for data analyses.

9.4.1. Intention-to-Treat (ITT) Population

This population includes all subjects assigned to treatment and will be used for sensitivity analysis of the primary efficacy endpoint.

9.4.2. Modified Intention-to-Treat (mITT) Population

This population consists of all enrolled subjects that took any portion of the study preparation. This population will be utilized for primary and secondary efficacy analyses and all safety analyses.

9.4.3. Per-Protocol Population

The per protocol (PP) population will consist of all subjects in the mITT population who consumed the entire bowel preparation solution and/or tablets and who have not violated the study eligibility criteria and have not deviated significantly from the protocol during the course of the study. This population will be utilized for the primary and secondary efficacy analyses. Any efficacy analyses from this population will be considered as supportive to the ITT and mITT analyses. Reasons for exclusion from the PP population will be defined prospectively in the statistical analysis plan and prior to unblinding of the data.

10. DRUG INVENTORY AND DISPOSITION

At the conclusion of the study, all drug materials will be accounted for. Federal law requires that, at the conclusion of the study, all drug materials must be returned to the study sponsor or destroyed according to local regulations.

11. STUDY MONITORING

A Braintree Laboratories Study Monitor or qualified designee will visit each study center prior to the commencement of the study and periodically during the course of the study in accordance with federal guidelines governing the sponsorship of studies.

12. DOCUMENTS AND NOTIFICATIONS

12.1. Informed Consent

Written informed consent will be obtained from the subjects by study personnel and will be kept on file at the study center. Documentation of the consent process should be noted in the study source documents.

12.2. Institutional Review Board

Peer review and approval of the protocol by an appropriate Institutional Review Board is required prior to commencement of enrollment. Amendments to the approved protocol must also be submitted to the Institutional Review Board and approved prior to their implementation.

12.3. Amendments to the Protocol

If Braintree Laboratories determines that there is need for an amendment, it will be produced in writing by Braintree Laboratories and will be made a formal part of the protocol following its submission and approval from the IRB.

